14.5 Relationship of Adverse Events to Investigational Medicinal Product

The causal relationship of the AE to study drug will be determined as either 'a reasonable possibility' or 'no reasonable possibility,' and will be defined as having either 1 of the following:

- **Reasonable Possibility:** The relationship of the clinical event to the study drug makes a causal relationship possible, and other drugs, therapeutic interventions, or underlying conditions do not provide a sufficient explanation for the observed event.
- **No Reasonable Possibility:** The relationship of the clinical event to the study drug makes a causal relationship unlikely, or other drugs, therapeutic interventions or underlying conditions provide a sufficient explanation for the observed event.

14.6 Clinical Laboratory Abnormalities, and Other Abnormal Assessments

The Investigator will exercise medical judgment in deciding whether abnormal laboratory test results are clinically significant. Laboratory abnormalities which are clinically significant will be recorded as AEs or SAEs.

If an abnormal laboratory value or assessment is clearly related to a medically defined diagnosis or syndrome, the diagnosis or syndrome will be recorded on the AE form, not the individual laboratory values.

All 'abnormal, clinically significant' laboratory results or assessments will be followed until they resolve (return to normal or baseline values) or stabilize, or until they are judged by the Investigator to be no longer clinically significant. Repeat laboratory tests or measurements will be performed if needed.

The criteria for determining whether an abnormal objective test finding should be reported as an AE and include:

1. Test result is associated with accompanying symptoms, and/or
2. Test result requires additional diagnostic testing or medical/surgical intervention, and/or
3. Test result leads to a change in dosing (outside of protocol-stipulated dose adjustments), discontinuation from the study, significant additional concomitant drug treatment, or other therapy, and/or
4. Test result is considered to be an AE by the Investigator or Sponsor.

14.7 Recording and Reporting of Adverse Events

All AEs, regardless of the relationship to study drug, occurring from the time written informed consent is obtained from a subject until the end of the safety follow-up period or the withdrawal of the subject from the study, and any AEs or SAEs reported spontaneously through the end of the safety follow-up period, should be reported to the Sponsor or designee.

NOTE: Elective hospitalization or procedure/surgery planned before subject enrollment for a preexisting medical condition does not constitute an AE unless the underlying disease or condition worsens after signing informed consent.

At each study visit, after the subject has had an opportunity to spontaneously mention any problems, the Investigator should inquire about the occurrence of AEs. The questioning will be open-ended and non-leading.

All AEs will be recorded in the source documents and AE eCRF. The AE eCRF will contain a description of the event, date of onset, date of resolution, severity, treatment required, relationship to study drug, action taken with the study drug, outcome, and whether the event is classified as serious.

The Investigator will evaluate the severity of the AEs as defined in Section 14.4 and will assess the causality between the AEs and the study drug as defined in Section 14.5.

Pre-existing illnesses, which started before entry and is still ongoing at the start of the study, will not be considered AEs unless they worsen during the treatment period. Pre-existing conditions will be recorded as medical history.

If the Investigator becomes aware of any new safety information, or any safety information which appears to be either study or study drug related after the final follow-up period, then they must notify the Sponsor or the designee immediately.

14.8 Recording and Reporting of Serious Adverse Events or Hepatic Adverse Events of Special Interest

All SAEs and Hepatic AESI occurring from the time written informed consent is obtained from a subject until the end of the safety follow-up period or the withdrawal of the subject from the study must be reported to the Sponsor or the designee using the *Serious Adverse Event/Adverse Event of Special Interest (SAE/AESI) in a Clinical Study Form* within 24 hours of the Investigator becoming aware of the SAE/AESI. All SAE/AESIs must also be entered in the AE section of the eCRF as soon as possible.

The SAE/AESI report should be completed as thoroughly as possible, including an assessment of causality. All such reports will identify subjects by unique code numbers assigned to the study participants, rather than by the subjects' names, personal identification numbers, or addresses.

The reporting contact for SAE/AESIs by email is as follows:

Email: [REDACTED]

In case of any email problems, the SAE/AESI form will be sent to [REDACTED] via fax to:

Fax: [REDACTED] [REDACTED]

Reports of pregnancy, although not classified as an SAE, will be handled and reported as in Section 14.10.

The Sponsor will comply with the applicable regulatory requirements related to the reporting of Suspected Unexpected Serious Adverse Reactions (SUSARs) to the Regulatory Authorities and central IRB/IEC(s). The Investigator will be responsible for informing the local IRB/IEC(s) of SUSARs, as per local laws and requirements.

14.9 Follow-up of Adverse Events

The Investigator should follow up with subjects who experienced AEs/SAEs, until the event has resolved or stabilized, and any abnormal laboratory values have returned to baseline; or until there is a satisfactory explanation for the changes observed. In the case of death, if possible, a pathologist's full report should be supplied.

The reference safety information for this clinical study is the IB.

14.10 Pregnancy

If a female subject who has been exposed to the study drug becomes pregnant, the course and outcome of the pregnancy should be monitored and documented. Where possible, if a female partner of a male subject who has been exposed to the study drug becomes pregnant and the subject provides this information, then the pregnancy will be documented based on information provided by the subject.

A pregnancy that occurs in a subject who has been exposed to the study drug must be reported using the same timelines and contact details as an SAE (Section 14.8) by a paper *Pregnancy in a Clinical Study Notification Form*, although pregnancy alone will not be classified as an SAE. If the outcome of the pregnancy or an event occurs during the course of pregnancy that involves an SAE (e.g., a congenital anomaly), then the *Serious Adverse Event (SAE) in a Clinical Study Form* will also be completed.

Subjects who become pregnant while on study must be withdrawn from treatment, as described in Section 9.5.

14.11 Overdose

There is no known antidote for MT-7117. Any signs or symptoms of a possible overdose will be treated supportively. In the case of an emergency, standard emergency procedures and supportive medical care will be provided.

If the subject takes a dose which is greater or more frequent than that specified in the protocol (with or without associated symptoms), this overdose is an AE and must be reported to the Sponsor or the designee on the AE eCRF.

If the overdose results in AEs that meet serious criteria, the SAE must be reported to Sponsor or the designee immediately or within 24 hours of awareness using the *Serious Adverse Event (SAE) Form in Clinical Study* according to SAE reporting procedures (Section 14.8).

If the subject experiences any other associated symptoms as a result of the overdose, the Investigator will record this as a separate AE/SAE.

15 DATA COLLECTION AND PROCESSING

15.1 Independent Data Monitoring Committee

An external independent Data Monitoring Committee (iDMC) will be established to perform regular review of the safety data to ensure the ongoing safety of participating subjects until the last subject completes the double-blind treatment period. The frequency of data review will be described in the iDMC Charter. Analyses required for the iDMC's review will be performed by a Contract Research Organization as described in the iDMC Statistical Analysis Plan (SAP). The committee's composition and a description of its responsibilities will be provided in the iDMC Charter.

15.2 Data Collection

Subject data will be collected on individual eCRFs and will be substantiated by source documents (such as laboratory reports, medical records, or ECGs) at the Investigator site. All relevant data will be transcribed into the eCRF from source documents, entered into the study database directly from source documents, or transferred electronically to the study database. Where no printed or electronic source documents exist, data will be entered directly into the eCRF and the eCRF will be considered the source document.

Before the start of the study, the Investigator will complete a Delegation of Responsibility List. The Sponsor or designee will provide training for completion of the eCRF. The eCRF will be completed according to guidelines provided by the Sponsor or its designee in writing, electronically, and/or verbally.

Completed eCRFs will be reviewed by the Study Monitor for the study to ensure data accuracy, completeness, and consistency in accordance with the study monitoring plan and other relevant procedural documents. Any relevant discrepancies found during the eCRF review or during data validation and/or quality assurance reviews of the data by data management or other functions are to be clarified by the Investigator (or his/her designated personnel).

The Investigator or designee must record all required subject data using the previously specified data collection method defined by the Sponsor. An explanation must be documented for any missing data where required. The Investigator must sign and date a declaration on the eCRF attesting to his/her responsibility for the quality of all data recorded, and that the data represents a complete and accurate record of each subject's participation in the study. The data collected in the eCRF will be returned to the Sponsor, and an electronic copy will be retained by the Investigator.

15.3 Case Report Form Completion

The eCRF will be presented in an electronic casebook comprising a series of electronic forms. The Subject Number should always be indicated and date (and time, if applicable) of each assessment should be entered in the eCRF.

The eCRFs must be completed in timely manner so that this does not delay the ongoing data validation, review, and quality control. The final, completed eCRF for each subject must be signed and dated by the Investigator on the appropriate eCRF form to signify that he/she has reviewed the casebook and certifies it to be complete and accurate.

The eCRF will feature a special means for correcting errors in the previously entered data. A complete audit trail of the original entries, changes and deletions, session dates and times, and the credentials of the eCRF user who performed the operation will be maintained by the system.

15.4 Data Processing

The data collected on the eCRFs will be captured in a specially constructed and validated database. The data will be validated using both manual and electronic means. Clarification of data will be requested from the Investigator site as required. An audit trail of the original database entries, changes and deletions, session dates and times, and the credentials of the database user who performed the operation will be maintained by the system. The completed database will be quality assured and locked to prevent further changes. A full database extract will be made available for statistical analysis according to the methods outlined in Section 16 and the Statistical Analysis Plan (SAP).

AEs and medical history entries will be coded using the Medical Dictionary for Regulatory Activities (MedDRA). Concomitant medications will be coded using the World Health Organization (WHO) Drug Dictionary. Versions of the dictionaries used will be documented in the Data Management Plan and SAP.

15.5 The Impact of COVID-19

Since study subjects may not be able to come to the clinical site for protocol-specified visits, specific information on COVID-19 will be captured via eCRFs to explain the missed protocol-specified information due to COVID-19.

If any study procedures are deemed unsafe or in need of special precautions to safeguard the subject or others from the transmission of COVID 19, these will be documented in the TMF, and, if altered in any way relevant to data collection or interpretation, or statistical analysis, will be addressed in the final SAP.

16 STATISTICAL METHODS AND PLANNED ANALYSES

The SAP will detail the implementation of all the planned statistical analyses in accordance with the protocol. The SAPs may be revised during the study to accommodate amendments to the clinical study protocol and to make changes to adapt to unexpected issues in study execution and data that may affect the planned analyses. Any deviations from the planned analysis will be described and justified in a separate document and in the Clinical Study Report (CSR).

Database lock and statistical analysis takes place when the last subject completes the last visit occurs and includes all subject data collected at Week 56 visit or during the safety follow-up period visit (Week 56). The database lock will be associated with a designated SAP. The SAP will be approved and signed prior to the database lock.

16.1 Determination of Sample Size

The planned sample size of 72 is expected to provide power for the comparison between MT-7117 treatment group and placebo group for ACR CRISS score at Week 52. The calculation of sample size assumes a 2-sided alpha level of 0.05 and uses EAST (Version 6.5) for Wilcoxon Mann Whitney test. The randomized 72 subjects (36 subjects for MT-7117 and 36 subjects for placebo) with a 1:1 allocation ratio would provide 80% power to detect treatment difference of 0.35 (35% improvement on MT-7117 treatment group compared to placebo group) in ACR CRISS score at Week 52 with an associated standard deviation (SD) of 0.5.

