7.2 Study Endpoints

7.2.1 Primary Endpoint

- The ACR CRISS composite score (0-1) at Week 52.

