9.1 Number of Subjects

Approximately 72 subjects are planned to be randomized in this study (36 subjects in each treatment group).

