16.3.4 Efficacy Analysis

16.3.4.1 Analysis of Primary Efficacy Endpoints

The primary treatment comparisons of interest are the ACR CRISS score for MT-7117 treatment group compared with placebo group at Week 52.

ACR CRISS score is a composite endpoint assessed in a 2-step process that calculates the probability of improvement for each subject ranging from 0.0 (no improvement) to 1.0 (marked improvement) refer to Appendix 4 for further details.

The primary endpoint will be summarized using descriptive statistics with interquartile range. The distribution of ACR CRISS score may not be normal distribution. For ACR CRISS score at Weeks 16, 26, 39, and 52 the comparison between MT-7117 treatment group and placebo group will be performed using this non-parametric analysis method. The point estimates and 2-sided 95% CIs and associated P-values for the difference between the treatment groups will be obtained using the Hodges-Lehman estimator corresponding to Wilcoxon's rank sum test. This non-parametric analysis will be performed with multiple imputation method, assuming missing at random. A supportive analysis will be performed at the same way for the primary endpoints using the per-protocol set (PPS). As a secondary analysis for the primary endpoint, the same analysis method will be applied to the intent to treat (ITT) population but the patients' data after taking rescue therapy will not be included. This approach will be performed to investigate a sensitivity for the primary analysis.

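### The power statement pairs a 0.35 difference with an SD of 0.5 that a 0–1 score cannot have in both arms, and it allows nothing for missing Week 52 scores

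*Protocol*

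**What the plan says.** The primary endpoint is "The ACR CRISS composite score (0-1) at Week 52" (Protocol 7.2.1). Protocol 16.1 sets out the design inputs: "The calculation of sample size assumes a 2-sided alpha level of 0.05". For the method, the same section "uses EAST (Version 6.5) for Wilcoxon Mann Whitney test". Its power claim reads: "The randomized 72 subjects (36 subjects for MT-7117 and 36 subjects for placebo) with a 1:1 allocation ratio would provide 80% power". The target effect is 0.35, which the section glosses as a gain of 35 per cent over placebo. The spread is given as "in ACR CRISS score at Week 52 with an associated standard deviation (SD) of 0.5". The synopsis and SAP 3.3 carry the same text. No source is given for 0.35 or for 0.5, and the SD is not described as within-arm or overall.

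The 72 is a number to be randomized, not a number evaluable. Protocol 9.1 says: "Approximately 72 subjects are planned to be randomized in this study (36 subjects in each treatment group"). No dropout allowance appears in either document. For the primary analysis, Protocol 16.3.4.1 says: "This non-parametric analysis will be performed with multiple imputation method, assuming missing at random". SAP 7.1.2.1 adds a further route to a missing score: it is set to missing when the Step 1 entry in the CRF is missing or was not done.

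**The concern.** A variable confined to 0–1 reaches an SD of 0.5 only when its mean is 0.5 and every value is 0 or 1. Two arms with means 0.35 apart cannot both meet that condition, so the stated pair of inputs describes no possible pair of arms. Separately, crediting the power to all 72 randomized subjects assumes a complete Week 52 score for each of them.

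This is the only statement in either document of what the trial can detect. After a null result in a proof-of-concept study, a reader would take 0.35 as the smallest effect the trial could address. That reading may be wrong, and the text gives no means of judging by how much.

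A lesser point is that 0.35 is an absolute difference in score. The gloss of a 35 per cent improvement over placebo can be read as relative. With an assumed placebo mean of 0.4, a relative 35% would be 0.4 × 0.35 = 0.14.

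**Working it through.** **Inputs from the documents:** two-sided alpha 0.05, Wilcoxon–Mann–Whitney test, 36 per arm, difference 0.35, SD 0.5, score range 0–1.

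**1. The plan's figure, by Noether's formula with normal shift.**
- p = Φ(0.35/(0.5√2)) = Φ(0.495) = 0.690.
- N for 80% = (1.960 + 0.842)²/(3 × 0.190²) = 72.7, using the unrounded p.
- Power at N = 72: Φ(√(3 × 72) × 0.1897 − 1.960) = Φ(0.83) = 79.6%. Simulation on normal data gives 81.5%.

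The stated 80% reproduces.

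**2. The bound on the SD.** On 0–1 with mean m, the variance is at most m(1 − m). For means m and m + 0.35, the average of the two bounds peaks at m = 0.325. This gives √(0.325 × 0.675) = √0.2194 = 0.468, reached only if every score is 0 or 1. One arm alone can reach 0.5: with means 0.15 and 0.50 the largest SDs are 0.357 and 0.5, pooled 0.434. Reading 0.5 as the overall SD leads to the same place: 0.2194 + (0.35/2)² = 0.25, so an overall SD of 0.5 again means a within-arm SD of 0.468.

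**3. Correcting only the SD, 72 complete subjects, difference 0.35.**
- SD 0.468: p = Φ(0.747/√2) = 0.701, and power = Φ(14.70 × 0.2014 − 1.960) = 84.1%. A two-proportion calculation gives 85.9%, and a simulated Wilcoxon test on 0/1 scores gives 85.0%.
- SD 0.40: 92.6%.

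**4. Adding losses.** The loss rates are assumptions, and lost subjects are treated as if imputation recovered nothing. Noether power at 0.35:

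| Evaluable per arm (loss) | SD 0.5 (stated, not attainable) | SD 0.468 (maximum) | SD 0.40 |
|---|---|---|---|
| 36 (0%) | 79.6% | 84.1% | 92.6% |
| 32 (11%) | 74.8% | 79.7% | 89.5% |
| 29 (19%) | 70.6% | 75.7% | 86.4% |
| 27 (25%) | 67.5% | 72.7% | 83.9% |

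At SD 0.468, 80% power needs 65 subjects (Noether) or 62 (two-proportion), so a loss of about 10–14% uses up the margin: (72 − 65)/72 = 10% and (72 − 62)/72 = 14%.

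**5. Shape matters as well as SD.** Wilcoxon power is not fixed by mean and SD.
- All scores 0 or 1, means 0.325 and 0.675: about 85% with 36 per arm and 77% with 29.
- Logit-normal scores (assumed placebo mean 0.2–0.4, logit SD 3–7): a 0.35 difference gives a Mann–Whitney probability of 0.75–0.79. Noether then gives 95–99% with 36 per arm and 90–97% with 29. Direct simulation gives 97% or more and about 93–99%.
- Beta scores, means 0.325 and 0.675, SD 0.45: 97.9% with 36 per arm by simulation, against 86.6% from Noether at the same SD.

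**6. Difference detectable at 80%.**

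| Distribution | 36 per arm | 29 per arm |
|---|---|---|
| All scores 0 or 1 | about 0.32–0.33 | about 0.36 |
| Logit-normal, as above | 0.21–0.27 | 0.24–0.30 |

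**The case against.** The strongest reply is that nothing is miscalculated and the slip is on the safe side. That stands. The inputs give the stated power, every attainable SD is below 0.5, and with complete data every distribution checked has at least 80% power at 0.35. A reader might infer that the trial is underpowered for 0.35, or that the power claim is false. The documents do not support either. Power falls below 80% only near the all-0/1 extreme and only with more than about 10–14% of the information lost.

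A reader might also take the SD 0.5 column (about 75% and 71%) as the trial's power with missing data. Those figures keep the impossible SD and do not describe power at an attainable 0.35.

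The losses shown are pessimistic as well. Neither document gives a rate. Subjects who stop treatment are encouraged to stay for Week 52 assessments (Protocol 8.1 and 9.5), and SAP 8.2.1 imputes from CRISS scores at all visits, so Weeks 16, 26 and 39 can recover part of the information. Imputation does not in general recover all of it.

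Finally, the percentage gloss is loose rather than wrong if read as percentage points, since the score is itself a probability of improvement.

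The reply does not rescue the stated inputs. A conservative SD is still an impossible one, and where the result does come to 80%, an overstated SD and an omitted allowance happen to offset each other.

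**Conclusion.** The point holds as a defect in the stated inputs. SD 0.5 is unattainable as a common SD with a 0.35 difference on this scale (maximum 0.468), neither figure is sourced, and missing Week 52 scores are not allowed for. The two faults pull in opposite directions. At the largest possible SD with complete data, power at 0.35 is about 84–86%. With 29 per arm and no recovery by imputation it is about 76–77% at that extreme, and about 93–99% by simulation in the logit-normal cases. So 80% at 0.35 is not established: true power may lie on either side, and with complete data it is probably higher, which makes the detectable difference probably smaller than 0.35.

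The 0.468 bound needs no assumption beyond the 0–1 range. The power figures rest on the normal-shift, two-point and logit-normal models and on assumed loss rates.

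**What to change.** Amend Protocol 16.1, the synopsis and SAP 3.3 together.

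- Replace SD 0.5 with an attainable value (no more than 0.47), name the assumed score distribution, and give the source of the SD and of 0.35.
- State power at 0.35, or the difference detectable at 80%, for 36 evaluable per arm under one or two such distributions.
- Repeat this for a range of missingness labelled as assumed, saying how much imputation is taken to recover.
- Describe 0.35 as an absolute difference in score and drop the percentage gloss.
- Do not restate the target as a 0.69 probability that an MT-7117 score exceeds a placebo score unless ties are handled. That value comes from the impossible SD and assumes untied scores, whereas Step 1 of the index assigns exactly 0 to some subjects. With all-0/1 scores, 80% power falls near means of 0.335 and 0.665. There the strict probability is 0.665 × 0.665 = 0.44, and the tie-adjusted one is 0.5 + 0.33/2 = 0.665.

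The cost is wording in three places. The number of subjects, the alpha and the analysis do not change. The drawback is that one power figure becomes a range that depends on stated assumptions.
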